9.3 Randomization and Participant Numbering

Every potential participant who is prescreened by telephone according to the IRB-approved script will be assigned a seven-character alphanumeric Screening Number and recorded on the Screening Log. This number will begin with 'S5' to identify that it is a Screening Number. The next two digits represent the site number (e.g., '11'), followed by a three-digit screening identifier starting with '501'. The screening identifier will be assigned to each prescreened participant at a site sequentially. For example, the first Screening Number at Site 11 will be S511501 and first Screening Number at Site 12 will be S512501.

Each participant who passes Screening and is enrolled in the trial at Visit 0 will be assigned a seven-digit Participant Number. The first two digits will be '11'. The next two digits represent the site number (e.g., '11'), followed by a three-digit participant identifier starting with '001'. The Participant Number will be assigned to each enrolled participant at a site sequentially. For example, the first Participant Number at Site 12 will be 1112001. Eligible participants will be enrolled in the study and sequentially assigned an identification number. All participants will also be assigned a unique participant identifier within the database for use in analysis.

Participants will be randomized in 1:1 allocation in a blinded fashion to the MDMA-assisted psychotherapy group and the placebo plus psychotherapy group, stratified by clinical site. Randomization will be managed via an Interactive Web Randomization System (IWRS) based on

a centralized randomization schedule developed by an independent third-party vendor to maintain blinding.

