7.0 Sample Size and Power Considerations

The statistical power calculations were made by fitting an MMRM model to CAPS-4 data from the Phase 2 study MPI data to obtain covariance parameter estimates. CAPS-4 data was also converted to the CAPS-5 scale, by dividing the CAPS-4 score by 34 and multiplying by 20 to obtain the CAPS-5 score, and both methods came up with the same level of statistical power. The following inputs created the 90% statistical power estimate using the PASS 14 Mixed Models Repeated Measures module.

- a. N=47 per group (allowing for 3 dropouts per treatment group)
- b. Alpha = 0.0499
- c. 1000 simulations
- d. Change from baseline means of 5.5, 12.8, and 20.5 for placebo. Change from baseline means of 17.2, 31.1, and 37.4, for MDMA at visits 1, 2, and 3, respectively
- e. Two levels of treatment factor (MDMA, Placebo)
- f. Three within subject levels (3 treatment visits)
- g. Subject level variance = 335
- h. Variance of R (diagonal elements) = 280
- i. Rho = 0.5
- j. Unstructured covariance

Additional participants may be added to the sample size at the recommendation of the Data Monitoring Committee (DMC) from the results of an administrative interim analysis (Section 8.9) occurring after 60% of the *mITT* participants have completed a final assessment of the Primary Outcome (Visit 19) and terminated treatment.

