8.7.1 Primary Efficacy Analyses

The *de jure* estimand of treatment efficacy will be used to estimate the causal effect of MDMA-assisted psychotherapy on PTSD symptom severity in the intended population of patients with PTSD from any cause (Estimand 1 in Table 4). All efficacy analyses will be based on the *mITT* analysis set. The primary treatment comparison will be made at a 2-sided, 0.0499 level of alpha. The primary estimator of effects of initially randomized treatments will be the difference between groups in mean change in CAPS-5 Total Severity Scores from Baseline to 18 weeks after randomization (Visit 19). Least squares means from a restricted maximum likelihood (REML)-based mixed model for repeated measures (MMRM) will be used to compare treatment groups at Visit 19. CAPS-5 data collected after treatment discontinuation will not be included in the *de jure* estimand. Missing data will not be imputed. The model is specified as follows: Let Y_{ij} be the change in the CAPS-5 score from the i th participant at the j th visit, $i = 1, \dots, n$ and $j = 1, 2, 3$, corresponding to post-baseline visits 8, 13, and 19, respectively. The treatment variable X_i is the randomized treatment of the i th participant. The variables T_1 and T_2 , are variables indicating if the data from that record are from visit 13, or 19, respectively. Covariates included in the MMRM model are the continuous baseline CAPS-5 Total Severity Score and the binary variable indicating dissociative subtype at baseline. Investigative site is included as a fixed effect. The regression model is specified as follows:

$$Y_{ij} = \alpha + \beta_1 X_i + \beta_{21} T_1 I(j=2) + \beta_{22} T_2 I(j=3) + \beta_{31} T_1 X_i I(j=2) + \beta_{32} T_2 X_i I(j=3) + \beta_4 \text{Baseline_CAPS}_i + \beta_5 \text{DS}_i + \phi \text{Site}_i + \varepsilon_{ij}$$

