8.9 Administrative Interim Analysis

An unblinded administrative interim analysis is planned to be performed at a single time point after the first 60% of participants in the *mITT* set have completed the final CAPS-5 follow-up assessment and terminated treatment, including early termination participants who have

completed their final CAPS-5, and 100 participants have been enrolled. The objective of the administrative interim analysis is to conduct a sample size re-estimation. The key secondary endpoint will not be evaluated at the interim analysis. The detailed results of the interim analysis will not be revealed to the site staff, participants, IRs, or sponsor staff/designees except for a single designated sponsor representative from MAPS. The independent DMC statistician will perform the unblinded administrative interim analysis as described in the DMC Charter. In addition, procedures will be developed to ensure the blinding of the participant level data for parties outside of the Independent Statistical Group (ISG).

Sample size re-estimation: Based on the result of calculating conditional power using the estimated effect size from the first 60% of participants in the *mITT* set, the sample size may be increased. The table below shows the range of possible effect sizes that could be observed at the interim analysis and what the guidance from the DMC could be for the adjusted sample size.

Table 6: Observed Effect Sizes and Corresponding Sample Size for 90% Conditional Power Guidance at the Interim Analysis (N=60)

Effect Size	≤ 0.32	0.32	0.34	0.36	0.38	0.40	0.42	0.44
Mean Change	-	5.76	6.12	6.48	6.84	7.2	7.56	7.92
Conditional Power ^[1]	< 50%	52%	60%	67%	74%	80%	85%	89%
Increase in Sample Size to Restore 90% Conditional Power	No increase	240	180	140	110	70	40	10

[1] Conditional Power based on the alternative hypothesis effect size as observed in the first 60 subjects.

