For Table 6, the conditional power estimates and the numbers to increase the sample size to restore 90% conditional power were calculated in PASS version 14 using the module for two-sample t-tests, which is based on the conditional power definitions from Jennison and Turnbull [7]. Since the minimum effect size for all possible scenarios where the sample size would be increased achieves greater than 50% conditional power for N=60, the type-I error rate is preserved with this administrative sample size re-estimation method [8]. However, the sponsor has chosen to allocate 2% of the alpha (0.0001) for this unblinded administrative interim analysis to account for any possible downward bias in the variance estimate. At the time of the interim analysis, the independent unblinded statistician will fit the cleaned data on the first 60 participants to the primary analysis model to estimate the parameters. These parameter estimates will be input to the PASS 14 Mixed Model Repeated Measures module to re-estimate the power. If the power is less than 90% and more than 50%, the independent statistician will increase the sample size up to the point where the power reaches 90%. These results will be provided by the unblinded independent statistician to the DMC.

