The DMC will review the group-unblinded interim analysis results provided by the independent statistician and will give recommendations to the designated sponsor representative from MAPS. The designated sponsor representative from MAPS will provide written information to the trial organizer delegate of MPBC indicating how many participants, if any, to add to the IWRS but will not provide any information on the corresponding conditional power the additional participants are being added to achieve. Only the re-estimation of sample size will be completed at the interim analysis, this will not be used to drop or add treatment arms or doses, change entry criteria, change randomization ratio or change primary endpoint. The sponsor representative from MAPS will not be part of any trial decisions or administration after the sample size re-estimation has been communicated to MPBC who will continue to be the trial organizer. If the DMC reports a sample size increase to the independent statistician DMC member, they will increase the randomization cap from 100 to the new sample size within the IWRS accordingly. Thereafter, the IWRS will cap randomization at the increased sample size resulting from the interim analysis. If the interim analysis results in a sample size increase, it will not be revealed to the investigators, participants, or sponsor.

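### SAP 8.9 sets a 90% conditional-power target for sample size re-estimation but orders a calculation that appears to target ordinary power, and the two give different sample sizes

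*SAP*

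**What the plan says.** SAP 8.9 introduces the rule with the phrase "Based on the result of calculating conditional power using the estimated effect size from the first 60% of participants", after which the sample size may be raised. Protocol 14.2.3 carries the same sentence, and the Protocol synopsis also describes a conditional power analysis. Table 6 gives, for observed effect sizes from 0.32 to 0.44, the conditional power and the increase that returns it to 90%. Its footnote reads "Conditional Power based on the alternative hypothesis effect size as observed in the first 60 subjects", and the SAP says the entries came from the PASS two-sample t-test module. Later in SAP 8.9 the added participants are again linked to a conditional power they are meant to achieve.

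The instruction to the statistician uses another tool and another word. The primary model is fitted to the first 60 participants, and then "These parameter estimates will be input to the PASS 14 Mixed Model Repeated Measures module to re-estimate the power". If the result lies between 50% and 90%, N is raised until it reaches 90%. This instruction does not say conditional.

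SAP 7.0 used the same module for the planning calculation: "The following inputs created the 90% statistical power estimate using the PASS 14 Mixed Models Repeated Measures module". The inputs listed there are N, alpha, number of simulations, visit means, factor levels and covariance terms. There is no interim result among them.

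SAP 8.9 also argues that type I error is preserved because every scenario with an increase has conditional power above 50% at N=60. SAP 8.7.2 (item 2d) gives 11 March 2020 as the interim data cutoff.

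**The concern.** Conditional power is the chance that the final test rejects, given the 60 outcomes already in hand. Ordinary power is the chance that a fresh trial of size N would reject if the observed effect were the true one. Once the interim result is favourable, conditional power is the higher of the two, because the first 60 outcomes are already banked. A rule that raises ordinary power to 90% therefore asks for more participants than one that raises conditional power to 90%.

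This is an unblinded adaptation. If the text supports two calculations, two defensible sample sizes can follow from one interim result, and the choice falls to someone who has seen the treatment difference. The stated 90% conditional power may also not describe what was done, and the SAP's type I error argument depends on which calculation is followed.

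**Working it through.** **Inputs**
- Alpha: "The primary treatment comparison will be made at a 2-sided, 0.0499 level of alpha" (SAP 8.7.1), so z = 1.961.
- Interim: 60 in total (Table 6), 30 per arm under 1:1 allocation (Protocol 9.3).
- Planned final N: 100, from the instruction that "they will increase the randomization cap from 100 to the new sample size within the IWRS accordingly" (SAP 8.9).
- Table 6 mean change divided by effect size is 18 in every column (for example 5.76/0.32), so the effect sizes are standardized differences with SD 18.

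**Formulas**, with observed effect size d and information I = N/4 (15 at interim, 25 at N=100):
- Conditional power at the observed effect: CP = Φ[(Z₆₀√15 − 1.961√I + d(I − 15)) / √(I − 15)], with Z₆₀ = d√15.
- Ordinary power: Φ(d√N/2 − 1.961). For 90%, N = 4(1.961 + 1.282)²/d², rounded up to equal arms.

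**1. Does the ordinary-power formula stand in for the MMRM module?** SAP 7.0 has a third-visit difference of 37.4 − 20.5 = 16.9, variance 335 + 280 = 615 (SD 24.8) and 47 per arm. Then Φ(16.9/24.8 × √23.5 − 1.961) = 91.0%, or 90.5% with the t distribution. The SAP states 90%, so the proxy reproduces it without any interim statistic.

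**2. Does Table 6 reproduce?** Not from 60 in total. At d = 0.40, CP = Φ[(6.0 − 9.805 + 4.0)/3.162] = 52.5%, where the table prints 80%. One-sided alpha does not recover the column, nor does 60 per arm going to 100 per arm. All seven printed values do return if Z₆₀ is taken as d√30, as if 60 were the number per arm, while information stays at 60 of 100. At d = 0.40 this gives Φ[(8.485 − 9.805 + 4.0)/3.162] = 80.2%. Table 6 is therefore a conditional-power table whose interim Z is too large by √2.

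**3. The calculations side by side** (increase only if the figure at N=100 is between 50% and 90%):

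| ES | Table 6 as printed | CP from 30 per arm | Ordinary power |
|---|---|---|---|
| 0.32 | 52%, +240 | 28.4%, none | 35.9%, none |
| 0.34 | 60%, +180 | 34.0%, none | 39.7%, none |
| 0.36 | 67%, +140 | 40.0%, none | 43.6%, none |
| 0.38 | 74%, +110 | 46.2%, none | 47.6%, none |
| 0.40 | 80%, +70 | 52.5%, +136 | 51.6%, +164 |
| 0.42 | 85%, +40 | 58.7%, +112 | 55.5%, +140 |
| 0.44 | 89%, +10 | 64.7%, +90 | 59.5%, +118 |
| 0.50 | not listed | 80.3%, +38 | 70.5%, +70 |
| 0.56 | not listed | 90.8%, none | 79.9%, +36 |

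Using the t distribution changes the ordinary-power increases by about 2.

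**4. Splitting the gap.** At ES 0.40, Table 6 and the ordered step differ by 164 − 70 = 94. Of that, 164 − 136 = 28 comes from conditional v ordinary power and 136 − 70 = 66 from the √2 in Table 6. At ES 0.44 the split of 108 is 28 and 80. At ES 0.32 to 0.38 the opposite decisions come from the √2 alone.

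**5. Cut-offs.** Both calculations equal 50% at d = 1.961/5 = 0.392. The 90% points differ: (1.961 × 5 + 1.282 × √10)/25 = 0.554 for conditional power and (1.961 + 1.282)/5 ≈ 0.648 for ordinary power. Between these two values only the ordinary-power rule adds participants.

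**The case against.** The best defence is that SAP 8.9 orders one calculation and sends one result to the DMC, while Table 6 is offered only as guidance. That stands as far as it goes. A reader might infer that the DMC would be handed two rival sample sizes, but the text provides only for the model-based result to go to them. The defence does not settle which definition governs, because the conditional-power basis also appears outside the table, in SAP 8.9 and Protocol 14.2.3.

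A second defence is that power in the ordered step is shorthand for conditional power, since the surrounding sentences discuss nothing else. This cannot be excluded: that the step is unconditional is an inference from the module's inputs in SAP 7.0. If the shorthand was meant, however, the named tool as used there has no place for the 60 observed outcomes, so the text needs correcting on either reading.

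Third, SAP 8.9 refers to the DMC Charter, and Protocol 9.4 and 14.3 keep the precise rules confidential. The Charter is not among the documents and may be clear. Protocol 14.2.3 nevertheless names the SAP as holding the full details, so the SAP should agree with itself.

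Finally, the like-for-like difference between the two power definitions is mainly a matter of efficiency. That is fair.

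**Conclusion.** The concern holds. SAP 8.9 states a conditional-power target and orders a step that appears to use ordinary power, with nothing to say which prevails. Against the printed Table 6, one interim result can mean +240 or none (ES 0.32), +70 or about +164 (ES 0.40), and +10 or about +118 (ES 0.44). Those gaps should not all be charged to the conflict between rules, because Table 6 carries its own error. The conflict alone is worth about 28 to 36 participants for ES 0.40 to 0.56.

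On type I error, a reader might infer that nothing is at risk because both rules share a 50% floor. They share it (ES 0.392) only when conditional power is computed from 30 per arm. Table 6 as printed allows increases at ES 0.32 to 0.38, where that conditional power is 28% to 46%, so the SAP's premise fails if the table is followed. The opposite inference, that type I error was inflated, is not supported either. The documents do not show that the table was used, and under these assumptions the ordered step with its own 50% floor satisfies the premise.

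The figures assume balanced arms, complete data, and a Visit 19 contrast that behaves like a two-sample comparison. Dropout or covariate adjustment would shift both rules.

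**What to change.** State one rule in SAP 8.9: conditional power computed from the interim MMRM estimate at Visit 19 and its standard error, at the actual information fraction, with N raised to reach 90% only when conditional power at the planned N is between 50% and 90%. Rebuild Table 6 from that rule, extend it to the upper cut-off, and put the same rule in the DMC Charter.

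Since the SAP itself dates the interim data cutoff at 11 March 2020, the interim may already have been run. In that case do not change the rule retrospectively. Report which calculation was applied, the conditional power at the planned N, and the resulting N.

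The cost is wording and one recomputed table. Prospectively, the rule asks for fewer participants than the ordinary-power step. Relative to the printed Table 6 it asks for none at ES 0.32 to 0.38 and for more at 0.40 to 0.44.

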9.0 Data Monitoring Committee

A DMC with appropriate expertise in the conduct of PTSD clinical trials will act in an advisory capacity to monitor participant safety on a routine basis throughout the trial by reviewing safety and study data provided by an Independent Statistical Group. The DMC will also monitor individual participant tolerability. The composition of the DMC will include two clinician experts in PTSD clinical trials and a biostatistician.

The DMC may:

- Review the study protocol and informed consent documents, and plans for data monitoring
- Evaluate the progress of the trial, study data quality, timeliness, participant recruitment, accrual and retention, participants' risk versus potential benefit, and other factors that could affect the study outcome
- Implement the adaptive design aspects of the study at the interim analysis by reviewing the interim analysis results and making the appropriate decision to the independent statistician on sample size re-estimation
- Consider relevant information that may have an impact on the safety of the participants or the ethics of the study
- Make other recommendations to MAPS concerning continuation, termination or other modifications of the study based on their observations of the study.

A full description of the DMC duties will be detailed in the DMC Charter.

